4.8 Data Review

Protocol deviations (PDs) will be assessed following the CRO’s processes. PDs will be reviewed, classified and documented as important or non-important PDs periodically, after Year 6 (prior to first interim database lock), after Year 7 (prior to second interim database lock) and at the end of the study (prior to final database lock). Assignment of subjects to analysis sets will be documented. Any changes to the statistical analysis prompted by the results of the review of study data will be documented in an SAP amendment and, if applicable, in a supplement to this SAP.

5. Analysis Sets

5.1 Assignment of analysis sets

Final decisions regarding the assignment of subjects to analysis sets will be made during the review of study data and documented (see Section 4.8).

The following statistical analysis sets will be defined:

Full analysis set (FAS):

All women who completed the baseline visit of the study

Primary analysis set Year 6 (PAS Year 6):

All women in the FAS with an age of 35 years or younger at baseline visit (i.e., an age of 36 or younger at end of Year 6)

Primary analysis set Year 7 (PAS Year 7):

All women in the FAS with an age of 34 years or younger at baseline visit (i.e., an age of 36 or younger at end of Year 7)

Primary analysis set Year 8 (PAS Year 8):

All women in the FAS with an age of 33 years or younger at baseline visit (i.e., an age of 36 or younger at end of Year 8)

The age at baseline (required for PAS Year 6, PAS Year 7 and PAS Year 8) will be used as recorded at baseline (Visit 2). If the age at baseline was not recorded, it will be calculated as the difference between year of baseline visit and year of birth recorded at screening visit.

Safety analysis set (SAF):

The SAF is identical with the FAS, i.e. all women who completed the baseline visit of the study.

6. Statistical Methodology

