15.1.1.25 Modification 25: Collection of age at Baseline visit (Visit 2)

Rationale: Age at baseline will be needed for the statistical analysis. As baseline might be up to 6 months after screening, the age at screening should not be used as it may not reflect the age at baseline.

List of protocol sections affected by this modification:

- [Section 9.1 Tabular schedule of evaluations](#)
- [Section 9.2.3 Baseline – Visit 2](#)
- [Section 9.3.1 Demographic](#)

- [Section 10.2 Analysis sets](#)
- [Section 9.2 Visit description](#)

15.1.1.26 Modification 26: Revision of the definition for start of treatment period for the primary variable

A new term ‘extension treatment period’ is introduced. This period starts at Day 1 of Year 6 of Mirena. Variables collected on an ongoing basis will primarily be analyzed for the ‘extension treatment period’ starting at Day 1 of Year 6 of Mirena use, i.e., data collected between the baseline visit and Day 1 of Year 6 of Mirena use will be excluded.

Rationale: This enables the calculation of the Pearl Index for the period of extended use of Mirena beyond the five years. Change was requested by the FDA.

List of protocol sections affected by this modification:

- [Section 10.3 Variables and planned statistical analyses](#)
- [Section 10.3.1.1.1 Primary efficacy variable](#)
- [Section 10.3.1.2 Safety variables](#)
- [Section 10.3.2.1 Analysis of the primary variable](#)
- [Section 10.3.2.3 Analysis of safety variables](#)
- [Section 10.3.2.3.2 Bleeding pattern](#)

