6.1.3.1 Insertion procedure

The original indication for Mirena insertion (contraception, or contraception plus HMB) will be summarized descriptively.

The duration since Mirena insertion (at baseline visit) will be calculated as the difference between the Mirena insertion date and the baseline visit date.

For subjects with Mirena insertion on Feb 29th, 2012 or earlier, two leap years of 366 days will be considered between 2012 and 2017, i.e. duration since Mirena insertion will be calculated as:

$(\text{date of baseline visit} - \text{date of Mirena insertion}) / [(366 \times 2 + 365 \times 3) / 5]$.

For subjects with Mirena insertion after Feb 29th, 2012, one leap year of 366 days will be considered between 2012 and 2017, i.e. duration since Mirena insertion will be calculated as:

$(\text{date of baseline visit} - \text{date of Mirena insertion}) / [(366 \times 1 + 365 \times 4) / 5]$.

The duration of Mirena use since its insertion (at baseline visit) will be summarized descriptively as a continuous variable as well as a categorical variable:

- < 5 years minus 2 weeks
- 5 years minus 2 weeks, to 5 years
- > 5 years

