6.6 Covid-19 pandemic

Additional analyses (introduced prior to Year 7 database lock):

After the Year 7 and Year 8 database lock, subjects affected by the Covid-19 pandemic (due to COVID-19 related adverse event, COVID-19 related protocol deviations or premature discontinuation due to COVID-19 related reason) will be listed with corresponding details.

Furthermore, COVID-19 related protocol deviations will be summarized and listed, as well as premature discontinuation due to COVID-19 related reason.

In addition, scheduled visits (physical or phone) and missed visits will be summarized and listed by timepoint.

7. Document history and changes in the planned statistical analysis

- 05 Oct 2017 Final SAP v1.0
- 14 June 2019 Final SAP v2.0, with the following changes:
 - Section 4.1: Due to low number of subjects in HMB subgroup, only summary tables on disposition and demographics will be displayed with three columns (Contraception, Contraception and HMB, Total), but summary tables on study drug administration, efficacy, safety and pharmacokinetics will be displayed with one column (Total).
 - Section 4.3 / Section 4.7 / Section 6.4: Terminology harmonized (“non-treatment-emergent” changed to “pretreatment”).
 - Section 4.3 / Section 4.4 / Section 6.4.3 / Section 8: Reference to BPD updated as RD-SOP-1107.
 - Section 5.1: Derivation rule added how to calculate age at baseline, if not recorded on CRF.
 - Section 6.1.1: Post treatment pregnancy and return to fertility moved to new Section 6.4.6.6.
 - Section 6.1.3.3: Subgroups BMI, race and ethnicity added. Patient data listing to display time in days after Day 1 Year 6, rather than time in days after baseline visit.
 - Section 6.1.3.6: Reference to Section 6.2.1 added. Subgroups BMI, race, ethnicity and indication for Mirena use added.
 - Section 6.2.1, Table 4–1: For Overall PI, formulas to calculate the crude exposure time corrected (use baseline visit date, but not date of Day 1 of Year 6).
 - Section 6.2.1, Primary analysis: Subgroup categories for age at insertion corrected, and subgroups age at baseline, race and ethnicity added.

- Section 6.2.1, Primary efficacy variable: Analysis of ectopic pregnancies added.
- Section 6.2.2.2: Terminology corrected (“nominator” changes to “numerator”).

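### When age at Visit 2 is missing, the SAP 5.1 fallback can only err upwards, and may wrongly drop a few women at the cut-off age from the primary analysis sets

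*SAP*

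**What the plan says.** SAP 5.1 defines PAS Year 8 as "All women in the FAS with an age of 33 years or younger at baseline visit" and PAS Year 7 as "All women in the FAS with an age of 34 years or younger at baseline visit"; PAS Year 6 uses 35. The age used is the one recorded at Visit 2. "If the age at baseline was not recorded", then "it will be calculated as the difference between year of baseline visit and year of birth recorded at screening visit".

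Protocol 9.3.1 lists year of birth, age at Visit 1 and age at Visit 2 among the demographic items. It lists no full date of birth.

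Before Amendment 1 (20 September 2017) the protocol approximated every woman's baseline age by the same year difference. The amendment replaced this with age recorded at Visit 2. Modification 25 (Protocol 15.1.1.25) explains that "Age at baseline will be needed for the statistical analysis". It adds that screening age is unsuitable because baseline may be up to six months later. SAP Section 7 records for v2.0 (14 June 2019): "Derivation rule added how to calculate age at baseline, if not recorded on CRF".

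**The concern.** Subtracting calendar years gives completed age only if the birthday has already passed on the visit date; otherwise the result is one year too high. Age at baseline is all that separates the primary analysis sets from the FAS, so at the cut-off ages a one-year error removes an eligible woman from the primary Pearl Index (PI), with her exposure and any pregnancy. It can also move women between the age-at-baseline subgroups of SAP 6.2.1 (25 coded as 26, or 35 coded as over 35). If derived ages feed the age-at-insertion subgroups, the error carries over to them.

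Empty fields are plausible. Age at Visit 2 was not a scheduled item before Amendment 1. SAP 6.1.3.1 has a branch "For subjects with Mirena insertion on Feb 29th, 2012 or earlier"; with the five-year limit at Visit 2, any such woman had her baseline by about the end of February 2017, well before the amendment.

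**Working it through.** **1. The plan's own exposure figure.** Protocol 10.4 gives 350 women, 15% dropout and 832 woman-years (WY). Reading 15% as a yearly rate with mid-year person-time:

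350 × [(1 + 0.85)/2 + (0.85 + 0.7225)/2 + (0.7225 + 0.6141)/2] = 350 × 2.380 = 832.8 WY.

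This reproduces 832, or about 2.38 WY per woman. With E = 8.32 (in 100 WY), the upper 95% limit stays at or below 1 for at most 2 pregnancies. The Poisson probabilities are 76.7% at a true PI of 0.2 (stated 76%) and 54.5% at 0.3 (stated 55%).

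**2. Error of the fallback.** With uniform birthdays, the share overstated at a visit is the fraction of the calendar year still to run: 75% on 1 April, 50% on 1 July, 28% on 20 September. Averages over visit windows (the 2017 windows are assumptions):

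| Visits spread evenly over | Share one year too high |
|---|---|
| a full year | 1 − 1/2 = 50% |
| 1 January to 20 September 2017 | 1 − 0.72/2 = 64% |
| 1 July to 20 September 2017 | 1 − (0.50 + 0.72)/2 = 39% |

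The share understated is zero in each case.

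**3. Women lost from PAS Year 8.** Protocol 10.4 assumes about 10% aged 33-35 at screening: 0.10 × 360 = 36. Screening of women aged 34-35 closes once 10 have completed baseline (Protocol Section 6). Assume therefore 36 − 10 = 26 women aged 33, with 25-60% of ages missing; the documents give no source for that share.

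- Low: 26 × 0.25 × 0.5 = 3.3 women; × 2.38 = 7.7 WY (0.9% of 832).
- High: 26 × 0.60 × 0.5 = 7.8 women; × 2.38 = 18.6 WY (2.2%).

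With 39% and 64% in place of 50%, the range is 26 × 0.25 × 0.39 = 2.5 to 26 × 0.60 × 0.64 = 10.0 women. Fewer are at stake in PAS Years 6 and 7, since only about 10 women aged 34-35 are planned.

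**4. Effect on the PI.** If every age were missing, 13 women would be lost: E = (350 − 13) × 832/350 = 801 WY. The permitted count stays at 2, because that needs only 722 WY. The probabilities become 78.3% and 56.9%. They rise only because fewer pregnancies are expected against the same permitted count.

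Expected pregnancies among the women lost in step 3 are 0.077 × 0.2 = 0.015 to 0.186 × 0.3 = 0.056. If one did occur, it could show: 3 pregnancies in 832 WY give an upper limit of 8.77/8.32 = 1.05, whereas 2 in 813 WY give 7.22/8.13 = 0.89.

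**5. The alternative.** Baseline age must be either the screening age or one more, and either the year difference or one less. Take the age that satisfies both, and the lower value if two remain. With a screening-to-baseline gap of g years and visits spread over the year, age is understated in a share g − g²/2:

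- 60 days: 0.164 − 0.014 = 15%.
- 182 days: 0.499 − 0.124 = 37%.

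No 33-year-old is wrongly removed, but those shares of 34-year-olds under the fallback would be wrongly kept.

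**The case against.** The strongest objection concerns the remedy. Modification 25 says screening age should not stand in for baseline age, and its rationale does not criticise the year difference. The SAP rule never admits an over-age woman to a primary set, whereas the alternative sometimes does. This stands as a limit on the fix: screening age can serve only as a second-line input, constrained by year of birth and visit dates, after a query has failed. It does not rescue the year difference, which errs in about half of cases with even visit dates, against 15% to 37%.

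Data cleaning may also fill the gaps. Protocol 11.1 describes completeness checks with queries to sites, and SAP 4.8 and 5.1 have set assignment settled and documented at data review. That is fair, although neither document promises a query for this field.

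A reader might infer that everyone enrolled before Amendment 1 is affected. The documents do not support this. They do not show how many such women there are or whether their ages were entered later. The insertion-date branch in SAP 6.1.3.1 is a computing rule, not an enrolment count. Even under the fallback, set membership changes only at the cut-off ages, and only with a birthday still to come.

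A reader might also infer a biased PI. Wrongful removal depends on birth date and visit date, and the documents give neither a link to pregnancy risk. The PI analyses are repeated in the FAS, and SAP 6.2.1 lists every pregnancy with age and key dates, so none would vanish unseen.

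**Conclusion.** The point holds as a minor one. The stated rule is wrong in a known direction: exactly one year too high whenever the birthday follows Visit 2 in the calendar year, and never too low. Where it is applied it can remove eligible women from PAS Years 8, 7 and 6 at ages 33, 34 and 35 and misplace others in the age subgroups.

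The size given for PAS Year 8, about 3 to 8 women and 8 to 19 WY, rests on three assumptions: 26 women aged 33, 25-60% of ages missing, and even birthdays and visit dates. If no age is missing, the effect is nil. Precision is essentially unchanged throughout. The residual risk is an unlikely but visible one: a single pregnancy leaving the primary count through a derivation error.

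**What to change.** 1. Before assigning analysis sets, query sites for completed age at Visit 2 wherever the field is empty, at least for women with a year difference of 34, 35 or 36. Whether sites hold the full birth date in source is an assumption.

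2. In SAP 5.1 replace the fallback sentence with, for example: *If age at baseline cannot be obtained from the site, it will be taken as the age consistent with the recorded age at screening, the year of birth and the dates of Visits 1 and 2; if two ages remain possible, the lower will be used. Because Modification 25 cautions against screening age used alone, it enters only under these constraints.*

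3. Report how many ages were derived, by analysis set. Where membership remains ambiguous, show the PI with and without those women.

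SAP 6.2.1 already repeats the Year 6 and Year 7 PIs on the final database, so one correction reaches all three sets. The cost is a data query and a short SAP edit. The downside is that a few women who had just turned 34 may be kept in PAS Year 8.

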6.1 Population characteristics

6.1.1 Disposition

Subject disposition will be summarized by descriptive statistics:

- End of screening period (including primary/underlying reason for premature discontinuation)
- Subjects included in PAS Year 6, PAS Year 7 and PAS Year 8, respectively, and in the FAS and SAF
- Inclusion and exclusion criteria

- Important PDs
- End of treatment period (including primary/underlying reason for premature discontinuation)

6.1.2 Demographics

Analyses of demographics will be performed based on the PAS Year 6 (for the analysis after Year 6), PAS Year 7 (for the analysis after Year 7) and the PAS Year 8 (for the final analysis after 8 years), respectively. Furthermore, these analyses will be repeated for the FAS.

6.1.2.1 Baseline characteristics

Baseline characteristics will be summarized by descriptive statistics:

- Demographics
 - Age at baseline
 - Ethnicity
 - Race
 - Height
 - Weight
 - BMI
- Baseline characteristics
 - Educational level
 - Tobacco consumption
 - Alcohol consumption

6.1.2.2 Medical, reproductive and menstrual history

Medical, reproductive and menstrual history will be summarized by descriptive statistics:

- Medical history (displayed by Medical Dictionary for Regulatory Activities [MedDRA] system organ class [SOC], high level term and preferred term [PT])
- Reproductive and menstrual history
 - Age at menarche
 - Number of pregnancies
 - Number of ectopic pregnancies
 - Number of births

- Number of vaginal births
- Number of caesarean births
- Duration from last birth or induced/spontaneous abortion to insertion
- Absence of menstrual/withdrawal bleeding (during last 3 months)
- Intracyclic bleeding (during last 3 months)
- Average length of cycle

6.1.2.3 Previous and concomitant medications

All concomitant medications taken during the study (i.e. starting with the date of informed consent) as well as the extended use of Mirena (i.e. the study drug) with its date of insertion and indication at the time of insertion (contraception, or contraception plus HMB), will be recorded on the eCRF.

The extended use of Mirena (i.e. the study drug) will be summarized as described in Section 6.1.3, whereas all concomitant medications taken during the study (excluding the extended use of Mirena) will be summarized by World Health Organization (WHO) Drug Dictionary substance name.

6.1.3 Study drug administration and compliance

As described in Integrated Protocol Section 7.1, no study drug (Mirena) will be provided by the sponsor. Subjects will enter the ‘treatment period’ (starting at baseline visit) and the ‘extension treatment period’ (starting at Day 1 Year 6), respectively, wearing a Mirena that was inserted 5 years earlier and will continue its use for an additional 3 years, i.e. up to a total of 8 years.

6.1.3.1 Insertion procedure

The original indication for Mirena insertion (contraception, or contraception plus HMB) will be summarized descriptively.

The duration since Mirena insertion (at baseline visit) will be calculated as the difference between the Mirena insertion date and the baseline visit date.

For subjects with Mirena insertion on Feb 29th, 2012 or earlier, two leap years of 366 days will be considered between 2012 and 2017, i.e. duration since Mirena insertion will be calculated as:

$(\text{date of baseline visit} - \text{date of Mirena insertion}) / [(366 \times 2 + 365 \times 3) / 5]$.

For subjects with Mirena insertion after Feb 29th, 2012, one leap year of 366 days will be considered between 2012 and 2017, i.e. duration since Mirena insertion will be calculated as:

$(\text{date of baseline visit} - \text{date of Mirena insertion}) / [(366 \times 1 + 365 \times 4) / 5]$.

The duration of Mirena use since its insertion (at baseline visit) will be summarized descriptively as a continuous variable as well as a categorical variable:

- < 5 years minus 2 weeks
- 5 years minus 2 weeks, to 5 years
- > 5 years

6.1.3.2 Removal procedure

The ease of and pain during Mirena removal will be analyzed as described in Section 6.5.2.

6.1.3.3 Expulsion rates

As described in Integrated Protocol Section 9.6.3.9, total or partial expulsion of the Mirena must be reported as an AE. Furthermore, expulsions must be recorded on the eCRF page “Intrauterine System Removal” as “Totally expelled” and “Partially expelled and removed”, respectively.

The number of subjects with expulsion (at least partial, or total) of the Mirena during the ‘extension treatment period’ (starting at Day 1 Year 6) will be summarized in a frequency table, overall and by parity, BMI, race and ethnicity.

The time from Day 1 Year 6 to expulsion will be analyzed using the Kaplan-Meier estimator. If no expulsion occurred in a subject, this will be considered a censored observation and the stop date of study drug administration (as defined in Section 4.7) will be used as censoring date.

The estimated proportion of subjects with expulsion of the Mirena will be reported for the time points 6 months (5.5 years of Mirena use), 12 months (6 years of Mirena use), 18 months (6.5 years of Mirena use), 24 months (7 years of Mirena use), 30 months (7.5 years of Mirena use), and 36 months (8 years of Mirena use). The cumulative proportion will be estimated.

All subjects with partial or total expulsion of the Mirena will be listed. The listing will contain the parity status and the time in days after Day 1 Year 6 when the expulsion was discovered.

